
THERAPEUTIC SCHEME:
 
 - This is a French multicentre randomized phase II study, and patients will be recruited in around 20 French centers. - Unicancer in France will serve as regulatory sponsor and will perform the monitoring, data management and analyses - This is a double-blind placebo-controlled trial, with 5 cohorts: 
 Cohort A: Osteosarcomas Cohort B: Ewing sarcomas Cohort C: Chondrosarcomas Cohort D: Chordomas Cohort E: CIC-rearranged sarcoma 
159 patients who meet the eligibility criteria will be randomly assigned in a 2 : 1 ratio to the following treatment groups :
 
The Arm A:
 
For adult patients (≥ 18 years old), regorafenib (without exceeding 160 mg/d) once daily for the 3 weeks on / 1 week off plus Best Supportive Care (BSC) until progression (according to RECIST 1.1), intolerance or withdrawal of consent. If the treatment provides clinical benefit to the patient despite radiological progression, he may continue regorafenib following consultation with the coordinator and sponsor.
 
For children Age ≥ 10 years to < 18 years old and BSA ≥ 1.30 m², regorafenib (82 mg/m²) once daily for the 3 weeks on/1 week off (without exceeding 160mg/day) plus Best Supportive care (BSC) until progression (according to RECIST 1.1), intolerance or withdrawal of consent. If the treatment provides clinical benefit to the patient despite radiological progression, they may continue regorafenib following consultation with the study coordinator and sponsor.
 
The Arm B:
 
Placebo plus BSC until progression (according to RECIST 1.1) or unacceptable toxicity. Patients who have received placebo will receive open-label regorafenib after objective tumour progression has been documented.
 
Patients will be stratified at randomization according to histology.
 
TREATMENT DURATION: until progression confirmed by central review and investigator decision or unacceptable toxicity
				

E) STATISTICAL ANALYSIS

SAMPLE SIZE:

The number of patients to include has been calculated for the experimental arm only using a A'Hern's [A'Hern 2001] single-stage procedure for phase II trials (Similar to a Fleming phase II design [Fleming, 1982] but assuming an exact Binomial distribution). Then, the half number of patients has been added to form the placebo arm depending on the randomization ratio 2:1.

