Using hypotheses similar to those described above, the number of patients has been calculated as follows:

π is the true probability of success (non progressive patients at **8 weeks** under regorafenib treatment for osteosarcoma and Ewing sarcoma ; at **12 weeks** for chondrosarcoma):

- $\pi_0 = 0.40$ non progressive patients at 8 weeks (0.5 non progressive patients at 12 weeks for chondrosarcoma): the largest non progression proportion which, if true, would clearly imply that the Regorafenib does not warrant further investigation.
- $\pi_1 = 0.67$ non progressive patients at 8 weeks (0.75 non progressive patients at 12 weeks for chondrosarcoma): the smallest non progression proportion that would imply that Regorafenib warrants further investigation.

Assuming a type I error alpha of 0.05 and 80% power, the number of patients required in the experimental arm is 23 patients to reject the null hypothesis $H_0: \pi \leq \pi_0$ versus the alternative hypothesis $H_1: \pi \geq \pi_1$ in a one-sided situation. At the end of the study, Regorafenib will be considered as interesting for further investigation if at least 14 patients are non progressive after 8 weeks of treatment in the experimental arm (for osteosarcoma and Ewing sarcomas) and if at least 16 patients are non progressive after 12 weeks of treatment in the experimental arm for chondrosarcomas.

No formal comparison between the experimental arm and the control arm will be performed.

The placebo arm will only be used to strengthen the results obtained in the experimental arm (randomization avoids patient selection biases). Hence, more patients will be included in the experimental arm, using a 2:1 randomization ratio. Therefore each cohort will involve a total of **36 evaluable patients (24 + 12)**.

Using a similar design as for the other cohorts, the sample size for **chordomas** cohort has been calculated as follows:

π is the true probability of success (non progressive patient at **6 months** under regorafenib treatment):

- $\pi_0 = 0.40$ non progressive patients at 6 months : the largest non progression proportion which, if true, would clearly imply that the Regorafenib does not warrant further investigation. This hypothesis is based on Stacchiotti S *et al* 2012 work showing 6 month PFS rate = 50% ; IC95% (28.8 – 71.1)

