- $\pi_1 = 0.75$ non progressive patients at 6 months : the smallest non progression proportion that would imply that Regorafenib warrants further investigation. This hypothesis is supported by Bompas E *et al*. Ann Oncol 2015 showing 6 month PFS rate = 85.3% ; IC95% (60.7 – 95.1)

Assuming a type I error alpha of 0.05 and 80% power, the number of patients required in the experimental arm is 16 patients to reject the null hypothesis $H_0: \pi \leq \pi_0$ versus the alternative hypothesis $H_1: \pi \geq \pi_1$ in a one-sided situation.

At the end of the study, Regorafenib will be considered as interesting for further investigation if at least 10 patients are non progressive after 6 months of treatment in the experimental arm.

As for other cohorts, No formal comparison between the experimental arm and the control arm will be performed. The placebo arm will only be used to strengthen the results obtained in the experimental arm (randomization avoids patient selection biases). Hence, more patients will be included in the experimental arm, using a 2:1 randomization ratio.

Therefore chordoma cohort will involve a total of **24 evaluable patients (16+8)**.

Using a similar design as for the other cohorts and using the results of Regobone osteosarcoma cohort (Duffaud et al. Lancet oncol 2019) showing that median PFS on placebo was 4 weeks for osteosarcoma patients, the sample size **for CIC-rearranged** cohort has been calculated as follows: π is the true probability of success (non progressive patient at **8 weeks** under regorafenib treatment for CIC -rearranged sarcomas):

- $\pi_0 = 0.25$ non progressive patients at 8 weeks (like median PFS of 4 weeks): the largest non progression proportion which, if true, would clearly imply that the Regorafenib does not warrant further investigation.
- $\pi_1 = 0.55$ non progressive patients at 8 weeks (like median PFS of 9 weeks): the smallest non progression proportion that would imply that Regorafenib warrants further investigation.

Assuming a type I error alpha of 0.05 and 80% power, the number of patients required in the experimental arm is 18 patients to reject the null hypothesis $H_0: \pi \leq \pi_0$ versus the alternative hypothesis $H_1: \pi \geq \pi_1$ in a one-sided situation.

At the end of the study, Regorafenib will be considered as interesting for further investigation if at least 8 patients are non progressive after 8 weeks of treatment in the experimental arm.

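### The chordoma success rule of 10 out of 16 has an exact type I error of 5.8%, above the stated 5%; with 16 patients the cut-off that meets both stated limits is 11

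*Protocol*

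**What the plan says.** Section E (Statistical analysis, Sample size) sizes every cohort on the experimental arm alone with A'Hern's single-stage procedure, described as "Similar to a Fleming phase II design [Fleming, 1982] but assuming an exact Binomial distribution". For chordoma the null 6-month non-progression rate is 0.40 and the alternative is 0.75. The text continues: "Assuming a type I error alpha of 0.05 and 80% power, the number of patients required in the experimental arm is 16 patients", the test being made "in a one-sided situation". The decision rule is that regorafenib deserves further study "if at least 10 patients are non progressive after 6 months of treatment in the experimental arm". Eight placebo patients bring the cohort to 24 evaluable patients. The same section rules out a formal comparison between the arms.

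**The concern.** In an exact single-stage design, the sample size and the cut-off are a pair. The cut-off must be high enough to keep the false-positive rate at the null within alpha, and low enough to give the required power at the alternative. The pair of 16 patients and cut-off 10 looked one short on the cut-off.

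If so, the cohort can be declared positive on a result that does not reject its own null hypothesis at the stated level. As the protocol plans no formal comparison with placebo, no second test would catch this.

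**Working it through.** **Inputs, all from Section E, Sample size.** Exact binomial; one-sided alpha 0.05; power 80%; null rate p0 = 0.40; alternative p1 = 0.75; n = 16; cut-off r = 10.

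**Formulas.** With X ~ Binomial(n, p): type I error = P(X ≥ r | n, p0); power = P(X ≥ r | n, p1).

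**Step 1: does the exact method reproduce the protocol's other rules at n = 23?**
- Osteosarcoma and Ewing sarcoma, 14 of 23, 0.40 versus 0.67: alpha 0.0349, power 0.803.
- Chondrosarcoma, 16 of 23, 0.50 versus 0.75: alpha 0.0466, power 0.804.

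Both meet the stated limits, so the exact binomial reading is sound for these cohorts.

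**Step 2: the chordoma rule as written, 10 of 16.**

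P(X ≥ 10 | 16, 0.40) is the sum of the terms for 10, 11, 12, 13 and 14 or more:

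0.03918 + 0.01425 + 0.00396 + 0.00081 + 0.00013 = 0.0583

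This is above 0.05. Power, P(X ≥ 10 | 16, 0.75), is 0.9204. The one-sided 95% exact (Clopper-Pearson) lower bound for 10/16 is 0.391, just below the null rate of 0.40.

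**Step 3: which cut-offs would work?**

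| n | Cut-off | Alpha | Power | Both limits met? |
|---|---|---|---|---|
| 16 | 10 | 0.0583 | 0.920 | No (alpha) |
| 16 | 11 | 0.0191 | 0.810 | Yes |
| 16 | 12 | 0.0049 | 0.630 | No (power) |
| 15 | 10 | 0.0338 | 0.852 | Yes |
| 15 | 11 | 0.0093 | 0.686 | No (power) |
| 17 | 11 | 0.0348 | 0.893 | Yes |

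At n = 16, 11 is the only cut-off that meets both limits; the lower bound for 11/16 is 0.452. The smallest design that meets both is 10 of 15.

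**Step 4: could another method justify 10 of 16?**
- Normal approximation without continuity correction: z = (10 − 6.4)/√(16 × 0.40 × 0.60) = 3.6/1.960 = 1.837, tail 0.033. This passes.
- With continuity correction, using 9.5 in place of 10: tail 0.0568. This fails.
- Mid-p: 0.0191 + 0.5 × (0.0583 − 0.0191) = 0.0387. This passes.

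The two variants that pass are not the exact binomial tail that the protocol says it uses.

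**Step 5: where do the two rules differ in practice?** They disagree only at exactly 10 successes. That outcome has probability 0.0583 − 0.0191 = 0.039 if the true rate is 0.40, and 0.9204 − 0.8103 = 0.110 if it is 0.75.

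**The case against.** The arithmetic is hard to dispute; the fair objections concern weight, cause and remedy.

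- **Size.** The excess is 0.8 percentage points, about 1.17 times the permitted 5%, in a 16-patient phase II cohort whose only decision is whether to study the drug further. The lower bound of 0.391 against 0.40 is a near miss. This stands. The rule with 11 has about a third of the false-positive rate of the rule with 10, but that comparison flatters the change, because 11 of 16 uses well under half of the allowed alpha. The fair statement is 5.8% against 5%.
- **Cause.** A cut-off of 10 is right for n = 15, so a patient may have been added without moving the cut-off. There is another explanation. The uncorrected normal critical value, n·p0 + 1.645·√(n·p0(1 − p0)), is 13.06, 15.44 and 9.62 for the cohorts above and 7.52 for CIC-rearranged sarcoma (n = 18, p0 = 0.25). Rounded up, these give 14, 16, 10 and 8, the protocol's own cut-offs. The document does not settle the cause, and the finding does not depend on it.
- **Remedy.** Raising the cut-off lowers power from 92.0% to 81.0%, so the chance of missing a drug with a true rate of 0.75 rises from 8% to 19%. This is a real cost, though 81% still meets the stated target. A required number of 15 with cut-off 10 would be equally valid, with 16 enrolled to suit the 2:1 ratio, as cohorts A to C require 23 and plan 24.

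None of this reconciles the stated alpha, sample size and cut-off.

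**Conclusion.** The concern holds. Under the protocol's own method and inputs, at least 10 of 16 has a one-sided type I error of 5.8% against the stated 5%. The result rests on no outside assumption, only on taking the exact binomial statement at its word and on 16 evaluable patients in the regorafenib arm. The excess is modest and affects the conclusion at one result only, 10 of 16. It still needs correcting, because this is the cohort's sole formal rule and a compliant cut-off exists at the planned sample size.

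**What to change.** Change the chordoma rule to at least 11 non-progressive patients out of 16 (alpha 0.0191, power 0.810). This changes one number and leaves the 16 + 8 patients as they are. The cost is the 11-point fall in actual power, to just above target.

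Tie the cut-off to the number evaluable in the regorafenib arm, since the margin is thin:
- **17 evaluable:** 11 (alpha 0.0348, power 0.893).
- **16 evaluable:** 11.
- **15 evaluable:** 10 (alpha 0.0338, power 0.852).
- **14 evaluable:** no cut-off meets both limits; 9 gives alpha 0.0583 and 10 gives power 0.742.
- **13 evaluable:** none again; 9 keeps alpha at 0.0321 with power 0.794.

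For 14 or fewer, state in advance which limit gives way; holding alpha would be consistent with the stated test. If the sponsor prefers 10 as the cut-off, the required number should be given as 15 and the 15 patients who count should be pre-specified. Either change should be made before any chordoma outcome data are seen.

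The CIC-rearranged sarcoma rule should be checked at the same time. By the same calculation, 8 of 18 with 0.25 versus 0.55 has alpha 0.0569, and there the next cut-off, 9 of 18, has power of only 0.747.

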No formal comparison between the experimental arm and the control arm will be performed. The placebo arm will only be used to strengthen the results obtained in the experimental arm (randomization avoids patient selection biases).

Hence, more patients will be included in the experimental arm, using a 2:1 randomization ratio. Therefore, **CIC-rearranged** cohort will involve a total of **27 evaluable patients (18+9)**.

F) TRIAL DURATION

INCLUSION PERIOD: Approximately 96 months (8 years)

TREATMENT PERIOD: until progression confirmed by central review or unacceptable toxicity: 6 Months (estimate)

Follow-up period: 18 months

OVERALL TRIAL DURATION: Approximately 10 years

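### CIC-rearranged cohort: the 8-of-18 rule has a one-sided type I error of 5.7%, and no cut-off at 18 patients gives both 5% alpha and 80% power

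*Protocol*

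**What the plan says.** Section E of the protocol (Sample size) sizes each cohort on the experimental arm alone, using A'Hern's "single-stage procedure for phase II trials (Similar to a Fleming phase II design [Fleming, 1982] but assuming an exact Binomial distribution"). Half as many patients are then added for placebo, to give 2:1 randomisation.

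For the CIC-rearranged cohort the same section sets:

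- a null rate of 0.25 without progression at 8 weeks, matched to a median PFS of 4 weeks;
- an alternative rate of 0.55, matched to a median of 9 weeks;
- alpha 0.05 and 80% power, "in a one-sided situation".

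It concludes that "the number of patients required in the experimental arm is 18 patients to reject the null hypothesis". Regorafenib is to be taken further "if at least 8 patients are non progressive after 8 weeks of treatment in the experimental arm". The cohort total is "27 evaluable patients (18+9"), and no formal comparison with placebo is planned.

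**The concern.** A single-stage exact design is a pair: a sample size and a cut-off that together meet the alpha and power targets. Because the binomial is discrete, adding one patient without revisiting the cut-off can push the type I error over its limit. The protocol gives every element of this pair for the CIC-rearranged cohort, so it can be checked directly, and the pair does not deliver the stated alpha.

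What is at stake is the verdict at the boundary. The arms are not formally compared, so the count in the regorafenib arm is the cohort's whole go/no-go rule. If exactly 8 of 18 patients are progression-free, the protocol declares the drug of interest on data that do not reject its own null at its own level.

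**Working it through.** **Inputs** (all from section E, Sample size): null rate p0 = 0.25; alternative rate p1 = 0.55; one-sided alpha 0.05; power 80%; n = 18 in the experimental arm; success if X ≥ 8; exact binomial distribution.

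**Formula.** For n patients and cut-off r, type I error = P(X ≥ r | n, p0) and power = P(X ≥ r | n, p1), where P(X ≥ r | n, p) = Σ over k from r to n of C(n,k) p^k (1−p)^(n−k).

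**Step 1: the plan's own rule, 8 of 18.**

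- Type I error = P(X ≥ 8 | 18, 0.25) = 0.0569, against a stated 0.05.
- Power = P(X ≥ 8 | 18, 0.55) = 0.8720, against a stated 80%.

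Power is met and alpha is not. The stated design is not reproduced.

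**Step 2: other cut-offs at n = 18.**

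| Cut-off | Type I error | Power | Meets both? |
|---|---|---|---|
| 7 | 0.1390 | 0.9463 | no (alpha) |
| 8 | 0.0569 | 0.8720 | no (alpha) |
| 9 | 0.0193 | 0.7473 | no (power) |
| 10 | 0.0054 | 0.5778 | no (power) |

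Both columns fall as the cut-off rises. Alpha first drops below 0.05 at 9, where power is already under 80%. No cut-off at n = 18 meets both targets.

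**Step 3: the design the method returns.** For each n, take the smallest cut-off with type I error ≤ 0.05.

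| n | Cut-off | Type I error | Power |
|---|---|---|---|
| 16 | 8 | 0.0271 | 0.7441 |
| 17 | 8 | 0.0402 | 0.8166 |
| 18 | 9 | 0.0193 | 0.7473 |
| 19 | 9 | 0.0287 | 0.8159 |
| 20 | 9 | 0.0409 | 0.8692 |

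The smallest n that meets both targets is 17, with cut-off 8. So 18 is not the number the stated method gives, although it is only one patient above it.

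**Step 4: a just-positive result.** At 8 of 18 (44.4%) the exact one-sided p-value against 0.25 is 0.0569. The exact one-sided 95% lower bound is the 5th percentile of a Beta(8, 11) distribution, which is 0.244 and lies below 0.25.

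**Step 5: other readings.**

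- Fleming's normal approximation at n = 18: 18 × 0.25 + 1.645 × √(18 × 0.25 × 0.75) = 4.5 + 3.02 = 7.52, so the cut-off would be 8. With a continuity correction of 0.5 it is 8.02, so 9. The protocol names the exact binomial, so the uncorrected value does not support the rule.
- Rates from the quoted medians under an exponential model: 0.5^(8/4) = 0.25 and 0.5^(8/9) = 0.540. The null is unchanged, so the type I error stays at 0.0569; power at cut-off 8 becomes 0.853.
- Reading the rule as more than 8 gives cut-off 9, with power 74.7%.

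**The case against.** The strongest reply is that this is a small slip with an obvious cause. The correct design is probably 8 of 17. Since 17 cannot be halved for a 2:1 ratio, 18 + 9 was used. The same section does something similar for the first three cohorts, where 23 are required and 24 + 12 planned. The arm is not too small, power is above target, and alpha is over by only 0.7 percentage points in a phase II activity screen. The null is itself a rounded planning value taken from osteosarcoma placebo patients: at a true rate of 0.24 the same rule has a false-positive probability of 0.046. The verdict changes only at exactly 8 of 18.

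Most of this stands as a statement of proportion. The sample size alone is not a problem, and there is one fault, a mismatch between n and cut-off, rather than two. The boundary lower bound of 0.244 is the same fault seen from another side.

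The reply does not remove the fault. The rounding is an inference: for this cohort the protocol calls 18 the required number, and 18 + 9 the evaluable number, so the cut-off of 8 applies to 18. Nor does the protocol state the alpha actually attained.

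**Conclusion.** The concern holds. As written, the CIC-rearranged rule has a one-sided type I error of 5.7% rather than 5%, with power of 87%, and no cut-off at 18 patients delivers the stated pair. The required number under the stated method is 17. The excess is modest and matters in practice only if exactly 8 of 18 patients are progression-free, but this is the cohort's sole pre-specified decision rule and its stated error rate is wrong.

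The conclusion rests on the protocol's own inputs: exact binomial, one-sided test, rates of 0.25 and 0.55, and 18 evaluable patients on regorafenib. That 18 came from rounding 17 up is an assumption, and the conclusion does not depend on it.

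**What to change.** Choose one of the following, without sight of the cohort's outcome data, and amend section E to match.

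1. **Keep 8 of 18** and state the operating characteristics as type I error 5.7% and power 87%. This is the smallest change.
2. **Set the cut-off by number evaluable:** at least 8 if 17 are evaluable, at least 9 if 18 are. Alpha then stays below 5%, but power at 18 must be stated as 75%, about 5 points under the 80% target.

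Under either option, change the required number from 18 to 17 and say that 18 is used to fit the 2:1 ratio. Under option 2, also reword the cohort total so that it does not presuppose 18 evaluable patients.

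Both options are wording changes with no extra patients; the cost is one less favourable stated figure, alpha in the first and power in the second. If both targets must hold at the planned number, 9 of 20 does so (alpha 0.041, power 0.869). At 2:1 that means 20 + 10 = 30 patients, three more than the planned 27, and a trial total of 162 rather than 159.
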